24 HOUR SPONSOR MEDICAL MONITOR

[REDACTED]

SAFETY REPORTING

[REDACTED]

SAFETY LABORATORIES

[REDACTED]

STATISTICS

[REDACTED]

ANALYSIS OF PHARMACODYNAMIC BLOOD SAMPLES

[REDACTED]

And

[REDACTED]

[REDACTED]

	
 • Geometric mean fold increase in antibody concentration. • Seroconversion rate (proportion of subjects with fold increase above threshold at any time post vaccination). • Proportion of subjects achieving antibody concentrations above specific thresholds at Days 29 & 85 (these will be 2, 4, 8 µg/mL). This will provide an assessment of the immune response to the first and second doses. 									
Study Design:	
This is a Phase I, randomised, double-blind, placebo-controlled, parallel group, single centre study.
 
There will be 2 cohorts of 30 subjects. Cohort 1 will receive two 0.5 mL injections, 4 weeks apart, each consisting of 25 µg of GBS-NN and 25 µg of GBS-NN2 (24 subjects) or placebo (6 subjects). Cohort 2 (30 subjects) will receive two 0.5 mL injections, 4 weeks apart, each consisting of 50 µg of GBS-NN and 50 µg of GBS-NN2 (24 subjects) or placebo (6 Subjects). All vaccines will be adsorbed to 500 µg Al3+ as Alhydrogel®.
 
Safety will be assessed after all subjects have completed Visit 4 (Day 8) for Cohort 1, at which point the decision will be made as to whether proceeding with administration of the doses in cohort 2 is appropriate.
									
Study Duration:	Study start is defined as check-in to the study unit on Day 1. Each individual subject will be involved in the study for approximately 12 weeks (excluding the 28 day screening period and the 6 month safety follow up).									
Study Population:	60 healthy female subjects aged 18 to 40 will be randomised into 2 cohorts of 30 subjects.									
Investigational Medicinal Product and mode of administration	
GBS-NN/NN2 vaccine will be supplied [REDACTED]
 
The placebo vaccine will contain Alhydrogel® mixed with sterile dilution buffer.
									

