9.4 Allocation of Randomisation Numbers

Subjects will be allocated to treatment groups according to a randomisation code produced by ████████ using the PROC PLAN procedure of SAS® version 9.3.

Subjects will be numbered sequentially from 001 (i.e. 001, 002 etc.). Replacement subjects will be assigned the same randomisation as the subject they are replacing, however, 100 will be added to the number (i.e. 101 would replace 001 etc.).

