12.2 Treatment Period and Post-Study Period

Subjects will be administered the primary dose of the appropriate dose of GBS-NN/NN2 or placebo according to the cohort and dosing schedule described in section 10.1 at Visit 2 and a second dose will be administered at Visit 6. All cohorts will incorporate sentinel dosing of 2 subjects in each cohort for the primary dose only: 1 on active treatment and 1 on placebo. No further subjects in that cohort will be dosed until 24 hours after dosing the second subject, provided that there are no serious or unexplained safety issues as determined by the Investigator.

The decision to proceed with administration of the primary dose in the subsequent cohort will be made as described in Section 12.5.

The following assessments will be carried out at these visits:

Visit 2

A general medical review, vital signs, urine pregnancy test, urine drugs of abuse test and alcohol urine test will be performed to re-confirm eligibility. Eligible subjects will then be randomised to receive the appropriate treatment as per the randomisation list for the cohort. A pharmacodynamic blood sample will be taken to measure pre-existing antibody levels and to obtain Peripheral Blood Mononuclear Cells (PBMCs) to assess cellular responses, prior to

dosing. Blood sample for haematology and serum biochemistry will be taken. Vital signs will be recorded at pre-dose (within 60 minutes of dosing), 2 (± 0.25) and 4 (± 0.25) hours post-dose. A general medical examination (including an assessment of the injection site) will be performed prior to discharge to ensure the subject is fit for discharge. At discharge subjects will be provided with oral temperature kit and instructed to record a temperature if they feel unwell in the seven days post dose.

Visit 3

Visit 3 will be performed 24 hours (± 2 hours) after administration of the primary dose and an assessment of the injection site will be performed, vital signs will be recorded and AEs and concomitant medications will be reviewed.

Visit 4

Visit 4 will be performed 1 week (± 1 day) after administration of the primary dose. An assessment of the injection site will be performed, vital signs will be recorded, safety blood samples for haematology and biochemistry will be collected, urinalysis will be performed and AEs and concomitant medications will be reviewed.

Visit 5

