12.5 Safety Monitoring Board and Safety Data Review Meetings

Both cohorts will incorporate sentinel dosing of 2 subjects in each cohort for the primary dose only: 1 on active treatment and 1 on placebo. No further subjects in that cohort will be

dosed until 24 hours after dosing the second subject, provided that there are no serious or unexplained safety issues as determined by the Investigator.

The decision to proceed with administration of the primary dose the subsequent cohort will be made as follows:

- It is intended that safety will be assessed after at least 24 evaluable subjects in cohort 1 (sentinel and main dose groups) have completed Visit 4 (Day 8), at which point the decision will be made to proceed with administration of the primary dose in cohort 2.

At least 24 evaluable subjects are required to complete through to visit 4 in cohort 1, in order to provide sufficient data for a decision to dose escalate. If the required number of evaluable subjects is not obtained in cohort 1, then the safety review committee (SRC) must decide whether there is enough information present to make a decision or whether further subjects should replace the dropped subjects or if sufficient information exists to determine if the dosing of cohort 2 is appropriate. The decision of the safety monitoring board and the output of the safety review must be clearly documented after the meeting.

The following safety data will be reviewed:

- Clinical Laboratory Tests
- Vital signs
- Assessment of injection site reactions
- AEs

The SRC will include at least two voting members - the Principal Investigator and Sponsor's Medical Monitor. If a voting member is unable to attend a Safety Data Review Meeting, a designated back-up can attend on their behalf and act as a voting member. Designated back-ups must be agreed and documented in advance. Non-voting members may also be part of the SRC.

The SRC will meet in person or by teleconference at scheduled Safety Data Review Meetings at which the safety data will be reviewed. A summary of safety data will be provided for review prior to these meetings for the SRC to review.

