After review and discussion of all the data, the decision will be made on dose escalation and documented by signature of a Dose Escalation Approval Form by the voting members of the SRC. Minutes documenting the main points discussed and decisions made regarding dose escalation will be produced. The minutes will be agreed by all parties and filed in the site Trial Master File.

Progression to the next higher dose level will be stopped if any of the study stopping criteria are met as described in Section 12.7. Individual subjects will be discontinued from the study if they meet any of the individual subject stopping criteria as described in Section 12.6.

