15.2 Studied populations for each study part

The following populations will be taken into account for each study part:

- **Randomized Set (RAN):** All included subjects who are randomized at V2 to one of the two cohorts;
- **Safety Set (SAF):** All subjects from the SAF set who receive at least one dose of the study vaccine (or placebo) will be taken into account in the description of the population (demographic or baseline characteristics);
- **Immunogenicity Set (IG):** The subset of subjects from the SAF set who will receive at least one dose of the study vaccine (or placebo) with available pre- and post-vaccination titres.
- **Per Protocol Set (PP):** All subjects from the IG set who receive both doses of the study vaccine (or placebo) and provide evaluable samples for analysis of the IgG antibody response to the GBS-NN/NN2 vaccine at Day 85 (most important immunological endpoint) and do not violate the protocol.

The safety analyses will be performed on the SAF set. The immunological analyses will be performed on the IG set. The most important immunological endpoint (immune response on Day 85) will also be performed on the PP set if the number of subjects in the PP set differs by more than 5% from the number of subjects in the IG set.

Missing or incomplete data will not be replaced, unless otherwise specified (example: values strictly under the LLOQ for immunogenicity data).

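### The plan says women are randomised to the two cohorts, but only vaccine or placebo is randomised within a cohort; any 25 v 50 µg comparison is non-randomised and should be labelled so (minor)

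*Combined protocol and SAP*

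**What the plan says.** **Statements that cohort is randomised.** The Randomized Set in section 15.2 is "All included subjects who are randomized at V2 to one of the two cohorts". The synopsis (Study Population) and section 9.3 both state that "60 healthy female subjects aged 18 to 40 will be randomised into 2 cohorts of 30 subjects". The synopsis also calls the study randomised and parallel group.

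**What is done at Visit 2.** Section 9.4: "Subjects will be allocated to treatment groups according to a randomisation code produced by" a redacted party. Section 10.3 puts randomisation before dosing on the morning of Day 1. Section 12.2, Visit 2: "Eligible subjects will then be randomised to receive the appropriate treatment as per the randomisation list for the cohort". Each cohort has 24 vaccine and 6 placebo subjects (synopsis, Study Design), and section 10.1 assigns one dose level to each cohort.

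**When cohort 2 may be dosed.** The synopsis says "Safety will be assessed after all subjects have completed Visit 4 (Day 8) for Cohort 1", after which cohort 2 is considered. Section 12.5 asks for at least 24 evaluable cohort 1 subjects through Day 8, "at which point the decision will be made to proceed with administration of the primary dose in cohort 2". It adds: "Progression to the next higher dose level will be stopped if any of the study stopping criteria are met".

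**Dose comparisons.** The synopsis (Statistical Analysis) allows reactogenicity intensity to be compared between vaccine dose groups. Section 15.1.3 gives the immune response to different dosing regimens as its continuous example, with ANOVA or ANCOVA as possible methods, and leaves the detail to the SAP.

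**The concern.** Randomisation is what allows a difference between two groups to be read as an effect of treatment. If women were randomised to cohort, a 25 v 50 µg difference in IgG or reactogenicity would have that basis. If dose depends on when a woman enters, it does not: the contrast also carries any difference between the two entry periods in the women recruited, their prior exposure to GBS, or the running of the assay.

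The three statements give the dose contrast a randomised basis, and one of them is an analysis-set definition that could be carried unchanged into the study report. A reader relying on it could take a period difference for a dose effect.

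**Working it through.** **1. The plan's own figure.** 2 × (24 + 6) = 60, which agrees with section 9.3. The plan states no alpha, power or effect size for a dose comparison, so there is nothing further to reproduce.

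**2. Could cohort have been assigned by chance?**
- Randomisation is on the day of dosing (10.3) and uses the list for the cohort (12.2), so cohort is already known.
- Under section 12.5 at least 24 evaluable cohort 1 subjects must reach Day 8 before the decision. Day 8 is 7 days after Day 1, so the 24th of them is dosed at least 7 days before any cohort 2 subject. This falls to 6 or 5 days if the Visit 4 window is used in full (± 1 day in 12.2, ± 2 days in 12.4).
- Those 24 women had no chance of receiving 50 µg when randomised. Under the synopsis wording the same holds for all 30.
- Under the 12.5 wording up to 30 − 24 = 6 cohort 1 subjects, or replacements, could overlap with cohort 2. Section 12.5 also lets the safety review committee decide with fewer than 24 evaluable subjects. No randomisation between cohorts is described for anyone.

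That only vaccine or placebo is randomised is an inference from 9.4, 10.3, 12.2 and 12.5. No other reading fits same-day randomisation behind a safety decision.

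**3. Illustration of size.** Input from the plan: 24 vaccinees per dose. Assumptions, not in the documents: SD of log10 IgG 0.5 (range 0.4 to 0.6); a cohort shift d of 0.05, 0.10 or 0.15 log10 at Day 85; no true dose effect.

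- SE = SD × √(2/24) = 0.5 × 0.2887 = 0.1443.
- False dose ratio = 10^d.
- False-positive rate: two-sided 5% t test on 46 df, from the noncentral t distribution with noncentrality d/SE (0.346, 0.693 and 1.039 at SD 0.5).

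| Shift (log10) | False dose ratio | SD 0.4 | SD 0.5 | SD 0.6 |
|---|---|---|---|---|
| 0.05 | 1.12 | 7.1% | 6.3% | 5.9% |
| 0.10 | 1.26 | 13.6% | 10.4% | 8.7% |
| 0.15 | 1.41 | 24.6% | 17.4% | 13.6% |

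**4. What the concurrent placebo groups can show.** Subtracting each cohort's own placebo mean removes a common additive shift. In SD units the direct contrast has SE √(2/24) = 0.289. The placebo-anchored contrast has SE √(2 × (1/24 + 1/6)) = 0.645, which is 2.24 times larger. It is a check, but an imprecise one.

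**5. What a baseline covariate can do.** The 95% interval for the dose ratio at SD 0.5 is ×/÷ 10^(t × SE) = 1.95 unadjusted. With ANCOVA, SE is multiplied by √(1 − ρ²), giving 1.89, 1.79 and 1.61 at an assumed Day 1 to Day 85 correlation ρ of 0.3, 0.5 and 0.7 (45 df). The effect on a shift of 0.10 depends on where the shift arises:
- Absent at Day 1: the bias stays 0.10, and the false-positive rate is 11.0%, 12.3% and 15.8%, against 10.4% unadjusted.
- Equally present at Day 1 (equal SDs assumed): the bias becomes 0.10 × (1 − ρ), and the rate falls to 7.9%, 6.8% and 5.9%.

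So adjustment helps with a baseline difference and not with a shift unrelated to baseline.

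**The case against.** The strongest reply is that this is loose phrasing. Sections 10.3, 12.2 and 12.5 leave no doubt about how subjects are allocated, and the synopsis describes the safety decision alongside the loose wording. The dose tests are optional, no objective compares doses, and immunogenicity is secondary. The documents give no evidence of drift: there is one centre, one set of eligibility criteria, a validated ELISA (13.1) and a reference standard (15.4.3), and the minimum interval between cohorts is about a week. All of this stands, and it is why the point is minor. The assay controls limit an assay shift but do not exclude it, and they do not address who enters when; the actual interval is unknown.

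The reply does not remove the contradiction. A label placed later in the SAP would leave the statements in the synopsis, 9.3 and 15.2 uncorrected.

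A reader might infer more than the documents support:
- **That vaccine versus placebo is compromised.** It is not. That comparison is randomised within each cohort.
- **That dosing cohorts in sequence is a flaw.** The point concerns only how the allocation is described.
- **That the plan contains no caveat at all.** Most of section 8 and any separate SAP are not in the supplied text, so one can say only that no visible passage carries the label.
- **That omitting a Day 1 covariate is an error.** Section 15.1.3 already names ANCOVA and leaves the choice open; the point is one of precision.

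**Conclusion.** The concern holds as a minor one. The description of randomisation in the synopsis, 9.3 and 15.2 contradicts the allocation set out in 9.4, 10.3, 12.2 and 12.5. What changes is the inference that a 25 v 50 µg test or interval can support.

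The primary safety objective, the vaccine versus placebo comparison within cohort, membership of the Randomized Set (used for disposition in 15.4.1) and the descriptive summaries do not change.

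Confidence in the contradiction is high. The figures for size rest wholly on the assumed SD, correlation and shift. They show what a modest shift would do, not that one occurred.

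**What to change.** 1. **Synopsis and 9.3.** Replace the statement that subjects are randomised into two cohorts. Say that the cohorts are dosed in sequence and that subjects are randomised to vaccine or placebo within their cohort. Write of dosing rather than enrolment, because the documents make dosing, not screening or consent, conditional on the safety decision. First reconcile the two statements of that condition: all cohort 1 subjects in the synopsis, at least 24 evaluable in 12.5.
2. **15.2.** Define the Randomized Set as subjects randomised at V2 to vaccine or placebo within their cohort.
3. **15.1.3 and the SAP.** Label any 25 v 50 µg test or interval, for IgG or reactogenicity, as non-randomised and exploratory. Show each cohort's concurrent placebo results beside it as an imprecise check for drift.
4. **Optional, for precision only.** Where post-vaccination IgG is compared between groups, use the ANCOVA option already named in 15.1.3, with log10 Day 1 IgG as covariate. State that this does not replace the label in item 3.

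The cost is wording in the protocol and SAP. The covariate needs no new data, since at Visit 2 "A pharmacodynamic blood sample will be taken to measure pre-existing antibody levels". No visit, subject or dosing step changes.

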9.3 Planned Sample Size

60 healthy female subjects aged 18 to 40 will be randomised into 2 cohorts of 30 subjects.

At least 24 evaluable subjects in cohort 1 will be required to attend through to visit 4 in order to provide sufficient data for a decision to dose escalate in cohort 2. If the required number of evaluable subjects are not obtained in a cohort, then the safety review committee (SRC) must decide whether there is enough safety information available to make a decision or whether further subjects should replace the dropped subjects or if sufficient information exists to determine if the dosing of cohort 2 is appropriate.

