15.4.3 Secondary Endpoints (Immunological Endpoints)

The secondary objectives are:

- To evaluate the IgG antibody response to the GBS-NN/NN2 vaccine at Day 85 (most important immunological endpoint).
- To assess whether pre-existing antibody levels affect the vaccine-induced antibody response.

Immunological parameters measured to evaluate objectives

In order to evaluate these objectives, GBS-NN and GBS-NN2 specific IgG concentrations will be determined by ELISA against a reference standard human antibody preparation of known concentration as described in the laboratory protocol and used to derive the following parameters for each subject:

- Antibody concentrations specific for GBS-NN and GBS-NN2 at each sample point ($\mu\text{g/mL}$)
- Fold increases over pre-immunisation level (Day 1) in antibody concentrations at each sample point (ratio)

Specific Endpoints calculated from immunological parameters

These parameters will be used to derive the following endpoints at all time-points according to the treatment group:

- Geometric mean antibody concentrations specific for GBS-NN and GBS-NN2 in $\mu\text{g/mL}$ (with 95% CI).
- Geometric mean fold increase in antibody concentration (with 95% CI).
 - Seroconversion rate (proportion of subjects with fold increase above threshold at any time point post vaccination up to Day 85).
- Proportion of subjects achieving antibody concentrations above specific thresholds at Days 29 & 85 (these will be 2, 4, 8 $\mu\text{g/mL}$). This will provide an assessment of the immune response to the first and second doses.

The most important immunological end point will be the values of these end points at Day85, 12weeks after the administration of the first dose of vaccine.

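### The 5% trigger for the Day 85 per-protocol analysis is counted on whole analysis sets, so that analysis can be left out when up to 3 of the 24 women in one vaccine arm are excluded from PP

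*Combined protocol and SAP*

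**What the plan says.** Section 15.2 sets the default: "The immunological analyses will be performed on the IG set". Entry to IG needs "at least one dose of the study vaccine (or placebo) with available pre- and post-vaccination titres"; neither the second dose nor a Day 85 sample is required. PP is narrower: "All subjects from the IG set who receive both doses of the study vaccine (or placebo) and provide evaluable samples" at Day 85, without a protocol violation.

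The PP analysis is conditional. "The most important immunological endpoint (immune response on Day 85) will also be performed on the PP set", but only "if the number of subjects in the PP set differs by more than 5% from the number of subjects in the IG set". No condition by arm or cohort is stated. The same section says that missing data are not replaced, apart from specified cases such as values below the LLOQ.

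Section 15.4.3 gives Day 85 its weight: "The most important immunological end point will be the values of these end points at Day85". It derives those endpoints by treatment group. Section 15.1.3 allows comparisons of post-vaccination levels between groups.

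Two other sections bear on who ends up in IG but not in PP. Under Section 12.6, a woman who meets an individual stopping criterion gets no further vaccine but is followed for safety. Under Section 9.5, a woman who conceives between the doses is not given the second but attends all remaining visits.

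**The concern.** The trigger works at a different level from the results that it guards. It compares the sizes of two trial-wide sets, which include 12 placebo subjects, while the results are read in vaccine arms of 24. A few exclusions concentrated in one arm can be a small share of the trial and a noticeable share of that arm.

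The exclusions that matter are women who had one dose and gave a Day 85 sample. Sections 9.5 and 12.6 make such women possible by design, and stops for local reactions could plausibly cluster at one dose level. They count in the IG estimate of what is meant to be a two-dose response. If the trigger does not fire, the plan requires no Day 85 estimate without them, and the 25 µg and 50 µg arms could be diluted unequally.

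The count also measures the wrong thing. A woman with no Day 85 sample leaves PP and moves the count, yet contributes nothing to the Day 85 IG result. The rule can fire when the two results are nearly the same and stay silent when they differ.

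**Working it through.** **Inputs.** Section 9.3: "60 healthy female subjects aged 18 to 40 will be randomised into 2 cohorts of 30 subjects". The synopsis (Study Design) splits cohort 1 as "24 subjects) or placebo (6 subjects", and cohort 2 the same way. The threshold is the strict 5% of Section 15.2, with IG as the denominator because the difference is measured from the IG count.

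**Planned size.** 2 × (24 + 6) = 60, which reproduces the plan's figure. The document gives no power calculation.

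**Trigger.** Let k be the number of IG subjects not in PP. The PP analysis is not required while k/IG ≤ 0.05.

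| IG | Largest k without a trigger | k/IG | Next k | Share of a planned arm of 24 if all k fall there |
|---|---|---|---|---|
| 60 | 3 | 5.0% | 4/60 = 6.7% | 3/24 = 12.5% |
| 59 | 2 | 3.4% | 3/59 = 5.08% | 2/24 = 8.3% |
| 40 | 2 | 5.0% | 3/40 = 7.5% | 2/24 = 8.3% |

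For every IG from 40 to 59 the largest untriggered k is 2. If replacements raise IG to between 61 and 66, it is still 3.

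**Other readings of the rule.**
- With PP as denominator, 3/57 = 5.26% would trigger.
- Applied per cohort of 30, 1/30 = 3.3% would not trigger and 2/30 = 6.7% would, leaving at most 1/24 = 4.2% of an arm.
- Applied per vaccine arm, 1/24 = 4.2% would not trigger and 2/24 = 8.3% would.

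**Chance of concentration.** Given exactly three exclusions falling at random among 60, the probability that all are in the same vaccine arm is 2 × C(24,3)/C(60,3) = 2 × 2024/34220 = 0.118.

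**Dilution (assumed deficits).** Suppose k of 24 women have Day 85 IgG f-fold below the others. The arm's mean log concentration falls by (k/24) × log f, so its geometric mean is multiplied by f^(−k/24).

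| f | k = 3 | k = 2 |
|---|---|---|
| 2 | 0.92 | 0.94 |
| 4 | 0.84 | 0.89 |
| 10 | 0.75 | 0.83 |

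For the threshold endpoints (2, 4, 8 µg/mL), three women missing a level that all others reach would turn 100% into 21/24 = 87.5%.

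**The case against.** The strongest reply is that 12.5% is a boundary case. It needs an IG set of at least 60, exactly three exclusions and all three in one vaccine arm. One unreplaced loss from IG brings the maximum down to two women. This stands, and 12.5% should be read only as a ceiling.

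Second, counting over the whole trial is an interpretation. Section 15.2 is headed as applying to each study part. If that means cohort, two exclusions in a cohort trigger the analysis. But the document defines no study parts for this trial, so the plain reading is the overall count. The ambiguity itself needs settling.

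Third, a reader might infer that 12.5% of an arm could be non-compliant and go unseen. The document does not support that. PP also drops women without an evaluable Day 85 sample, who cause no dilution, and women with other violations may have a normal two-dose response. Section 15.4.1 requires the IG and PP counts, and Section 15.1.1 requires individual listings. Nothing forbids a PP analysis below 5%. Those counts and listings do not, however, supply a PP geometric mean with its confidence interval.

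Fourth, the effect may be small against sampling error. Assuming a log10 SD of 0.3 to 0.5 (none is given), the lower 95% limit for a geometric mean with n = 24 lies at about 0.75 to 0.62 of the estimate. Most of the factors above fall inside that. This limits the importance of the point, but a systematic shift in one arm is still worth showing.

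Last, the primary objective is safety (Section 7.1), and no decision rule uses the PP result. Section 15 also defers detail to an SAP whose text is not in the document, so an override there cannot be checked.

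**Conclusion.** The point holds in a limited form. As written, the rule can leave the two-dose Day 85 result unreported while one-dose women remain in an arm's IG estimate. The ceiling is 3/24 = 12.5% of a vaccine arm when IG is 60 (or slightly more with replacements), and 2/24 = 8.3% when IG is 40 to 59. This assumes the whole-trial reading with IG as denominator. Actual dilution also requires the excluded women to have given a Day 85 sample and to have responded less.

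The factors 0.92, 0.84 and 0.75 illustrate the size for three such women. The fold deficits behind them are assumed. Section 6.2.2 describes the earlier GBS-NN vaccine as highly immunogenic after two doses of 50 µg or one or two of 100 µg, which makes a dose-number effect plausible but gives no size.

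A reader might go further and conclude that the comparison of 25 µg with 50 µg is biased. The document does not support that: it shows that unequal dilution is possible, not that it is expected. For a secondary endpoint in a Phase I safety trial, this is a cheap, optional improvement.

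**What to change.** Delete the 5% condition from Section 15.2 and always report the Day 85 immunological endpoints on both IG and PP, by treatment/dose group. If a trigger is preferred, apply it within each treatment/dose group; in a vaccine arm of 24 it would then fire from the second exclusion. In either case, say what study part means in Section 15.2 or remove the term.

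The cost is one extra Day 85 table, sometimes nearly identical to the IG table. Both sets are already defined, and no new subjects, visits or samples are needed.
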